12. OTHER PLANNED ANALYSES

12.1 Quality of Life Analysis

Quality of Life (QoL) is assessed using the EQ-5D and AFEQT questionnaires. Quality of Life (QoL) status will be compared to baseline at 3 months, 6 months, 1 year, 2 years and 3 years. Descriptive statistics for the baseline and absolute values as well as changes from baseline of the scores (AFEQT overall score, AFEQT symptoms score, AFEQT daily activity score, AFEQT treatment concern score, AFEQT treatment satisfaction score, EQ-5D VAS)) at follow-up visits will be summarized by treatment groups. The analyses will be performed in the PP population. Cross-over subjects will be completely excluded for all QoL summaries.

Paired-sample t-tests will be used to test whether the change-from-baseline values differs from zero within each treatment group. A two-sample comparison of the two groups with respect to changes-from-baseline in QoL will be performed using a repeated measurement model, including the baseline value as a covariate and assessing treatment group differences. EQ-5D single items will be summarized descriptively in a frequency table by treatment group for baseline and follow-up visits. Changes from baseline in EQ-5D single items will also be presented for each follow-up visit in a frequency table. It will then be tested if there is a difference between test and control group using Wilcoxon-Mann-Whitney test separately for each follow up visit.

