## Appendix B: Guidelines and Restrictions for the ATTEST Protocol Regarding Cross-over from the Drug (Control) Group

1. Guidelines and principles for cross-over are to be followed by the investigator as laid down in this document and in the protocol.
2. It is the intent of the Sponsor and organizers of this study that cross-over be significantly reduced from published rates quoted in previous drug versus ablation trials.
3. The crossing over from the drug group undermines the tenets of equipoise that are intended in: (a) the study's collective inclusion/exclusion criteria for all subjects; (b) the eligibility of all subjects at study onset to be randomized to either treatment group; and, (c) the intended balance of AF severity, drug history, concurrent illnesses (HATCH score severity), demographics, and other characteristics, such that legitimate statements might be made in comparing the outcomes of medical management versus ablation therapy. The nature and conditions for cross-over from the Control (AAD therapy) Group to the Test (PVI) Group, in a randomized controlled study, are not well understood and are multi-factorial. Thus, any assumptions that subjects crossing over reflect the general demographics, disease severity, and extent of disease progression within either study group at randomization cannot be held with certainty.
4. One could justifiably argue that those most likely to suffer severe side effect reactions from AAD therapy might be those who take their drugs sporadically, take drugs sometimes too close together (shortened inter-dose time interval), suffer rebound effects from resumption of drugs after a drug holiday, and who do not heed the warnings of physicians/pharmacists about mixing drugs for AF/AT with those for other chronic diseases. One might further argue that those with heightened disease progression, as noted in published literature, would be among the oldest in their randomized study group and that their baseline HATCH scores are likely to be high as well, which is consistent with elderly patients. If one or more of these assumptions are true, those most likely to seek cross-over from the drug group would be among the aforementioned, resulting in a relatively younger, healthier, and more compliant group of subjects remaining in the drug group over the whole 3 year study period. In this context, extensive cross-over certainly would erode equipoise.

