7. ANALYSIS POPULATIONS

The following analysis populations will be used to complete the analyses of data.

Cross-over subjects will be handled differently for each type of analysis population, as described subsequently. In general, subjects from the control group who have an ablation procedure after the primary endpoint is met will not be analyzed as cross-over.

Intent to treat (ITT) population: The ITT subject population will include all

subjects randomized, where subjects will be classified by the group to which they are randomized, regardless of the treatment received. For the ITT population, cross-over subjects will be included in the Control Group per randomization. Lost-to-follow-up and withdrawn/early termination subjects will also be included in the ITT population.

Per protocol (PP) population: The PP subject population will include randomized subjects who satisfy the following criteria, according to the treatment actually received:

- **Test Group:** subjects who
 - have undergone RF ablation,
 - are treated with the study catheter (THERMOCOOL[®] Catheter Family),
 - are in compliance (no major protocol deviations that has an impact on scientific value of the study) with the study protocol, and
 - have been treated for the study-related arrhythmia.
- **Control Group:** subjects who
 - have started an investigator-prescribed AAD and completed the dose-loading period (2 weeks),
 - have not undergone RF ablation,
 - are in compliance (no major protocol deviations that have an impact on scientific value of the study) with the study protocol, and
 - have been treated for the study-related arrhythmia.

All analyses conducted in the PP population will be as treated analyses. For descriptive tables and simple inferential models with fixed treatment effects subjects who have undergone RF ablation will be included in the Test Group regardless of the original treatment assigned (original randomization). Thus, cross-over subjects will be included in the Test Group for PP analyses. For more complicated inferential analyses, models will be applied where treatment itself is included as time-dependent covariate (see section 10.2 and 10.6.4). The approach described above applies for all tables which do not summarize data by visit (e.g. for time to event endpoints and other endpoints calculated overall per-patient). For summaries by visit and repeated measurement models, cross-over subjects will be completely excluded.

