8. GENERAL ISSUES FOR STATISTICAL ANALYSIS

8.1 General Statistical Methodology

Descriptive summaries will be provided where appropriate for each of the primary and secondary variables. Tables in the ITT population will summarize data by randomized treatment, tables in the PP and Safety populations will summarize data by treatment actually received if not otherwise specified.

Primary and secondary effectiveness analysis will be conducted in the ITT and the PP populations. All safety data analyses will be performed in the Safety Population.

Health economic and QoL tables will be completed for the ITT population unless otherwise specified. According to the protocol it was planned to use the PP population for health economic and QoL tables, but this was changed to ITT population to perform the analysis based on the randomized treatment groups.

Continuous, quantitative, variable summaries will include the number of subjects (N) with non-missing values, mean, standard deviation (SD), median, minimum, maximum, and quartiles, unless otherwise specified.

Categorical, qualitative, variable summaries will include the frequency and percentage (where applicable) of subjects who are in the particular category. In general, the denominator for the percentage calculation will be based upon the total number of subjects in the study population for the treatment groups unless otherwise specified.

The baseline value will be defined as value entered to the screening/baseline page of the eCRF (terminology screening/baseline is not used consistently in eCRF, but there is only one screening/baseline assessment planned according to protocol).

All analyses will be performed using SAS[®] Software version 9.1.3 or later. ADDPLAN[®] version 5.0.2 or later and East version 5.3 or later may also be used.

For re-calculating of operating characteristics for the analyses of the primary endpoint, the software WinLD will be used.

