12.2 Health Economics Analysis

For this secondary health economic endpoint, health care utilization (number and length of hospitalizations and unscheduled cardiovascular-related visits), the total number and length of hospitalizations will be summarized by treatment groups in the ITT population.

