14.2.8	ITT, PP	New AAD Drugs – ATC classes	16.2.22	
14.2.9	ITT, PP	Heart Rhythm	16.2.17.3	
14.2.10.1	ITT, PP	Factors Associated With Time to Persistent AF/AT Results of Cox models with single baseline covariates	16.2.17.1	
14.2.10.2	ITT, PP	Factors Associated With Time to Persistent AF/AT Results of Cox model with multivariate baseline covariates	16.2.17.1	
14.2.10.3	PP	Factors Associated With Time to Persistent AF/AT Results of Cox models with single baseline covariates and treatment as time-dependent covariate	16.2.17.1	
14.2.10.4	PP	Factors Associated With Time to Persistent AF/AT Results of Cox model with multivariate baseline covariates and treatment as time-dependent covariate	16.2.17.1	
14.2.11.1	PP	Quality of Life – EQ5D Descriptive summary of VAS	16.2.14	
14.2.11.2	PP	Quality of Life – EQ5D	16.2.14	

Table Number	Population	Table Title / Summary	Supporting Listing	Interim Analysis Number
		Descriptive summary of changes from baseline in VAS		
14.2.11.3	PP	Quality of Life – EQ5D Results of repeated measurement model for changes from baseline in VAS	16.2.14	
14.2.11.4	PP	Quality of Life – EQ5D Frequency table for EQ-5D single items	16.2.14	
14.2.11.5	PP	Quality of Life – EQ5D Frequency table for changes from baseline in EQ-5D single items and results of Wilcoxon-Mann-Whitney test	16.2.14	
14.2.12.1	PP	Quality of Life – AFEQT Descriptive summary of derived scores	16.2.13	
14.2.12.2	PP	Quality of Life – AFEQT Descriptive summary of changes from baseline	16.2.13	
14.2.12.3	PP	Quality of Life – AFEQT Results of repeated measurement model	16.2.13	
14.2.13.1	ITT	Health Economic Analysis Number of hospitalizations	16.2.25	
14.2.13.2	ITT	Health Economic Analysis Length of hospitalizations	16.2.25	
14.2.13.3	ITT	Health Economic Analysis	16.2.25	

Table Number	Population	Table Title / Summary	Supporting Listing	Interim Analysis Number
		Number of unscheduled cardiovascular-related visits		

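### SAP 8.1 says the quality-of-life analysis moved from PP to ITT, but SAP 12.1 and all eight QoL table shells still use PP and drop every cross-over

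*SAP*

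**What the plan says.** SAP 8.1 sets the general rule: "Health economic and QoL tables will be completed for the ITT population unless otherwise specified". It then notes that the protocol had planned PP for these tables and explains that "this was changed to ITT population to perform the analysis based on the randomized treatment groups".

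SAP 12.1, the section that governs QoL, says: "The analyses will be performed in the PP population. Cross-over subjects will be completely excluded for all QoL summaries". It then plans tests between the arms: a repeated measurement model for change from baseline with baseline as covariate, and a Wilcoxon-Mann-Whitney test at each follow-up visit for the EQ-5D single items.

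The table list in SAP 15.1 labels every QoL table PP. One of them is Table 14.2.11.3, "Results of repeated measurement model for changes from baseline in VAS".

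For health economics, SAP 12.2 says "the total number and length of hospitalizations will be summarized by treatment groups in the ITT population", and Tables 14.2.13.1 to 14.2.13.3 are labelled ITT.

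SAP 7 defines how each population treats cross-overs. Under ITT: "For the ITT population, cross-over subjects will be included in the Control Group per randomization". Within the PP definition: "For summaries by visit and repeated measurement models, cross-over subjects will be completely excluded".

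**The concern.** SAP 8.1 describes a completed change and gives a sound reason for it. The section and shells that a programmer would follow do the opposite, so no ITT QoL table would be produced, while a reader of SAP 8.1 would believe that QoL had been compared as randomized.

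The population matters because SAP 12.1 goes beyond description and tests one arm against the other. Removing every Control subject who was later ablated selects that arm on an event after randomization, and nothing comparable is removed from Test. The protocol itself warns about this. Appendix B, item 3, says that it cannot be held with certainty, for "any assumptions that subjects crossing over reflect the general demographics, disease severity, and extent of disease progression", that cross-overs match either group at randomization. Item 7 ties the decision to cross over to severe AF symptoms or severe side effects, both of which plausibly bear on QoL. The comparison would therefore lose the protection of randomization on an outcome close to the reason for exclusion.

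**Working it through.** **Side-by-side reading**

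| Place | Health economics | QoL |
|---|---|---|
| Protocol 13.14 and 13.16 | PP | PP |
| SAP 8.1 | changed to ITT | changed to ITT |
| SAP 12.2 / 12.1 | ITT | PP, cross-overs excluded |
| SAP 15.1 shells | 3 of 3 ITT (14.2.13.1-3) | 8 of 8 PP (14.2.11.1-5, 14.2.12.1-3) |
| SAP 5.1, list of changes | not mentioned | not mentioned |

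The QoL shell count is 5 for EQ-5D plus 3 for AFEQT, which makes 8, and none is ITT.

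The handling of cross-overs in SAP 12.1 matches neither possible parent rule. Protocol 13.6 puts cross-overs in the Test Group for PP analyses. SAP 8.1 with the ITT definition keeps them in Control. SAP 12.1 drops them. This agrees with the SAP 7 by-visit rule for PP, so it is coherent within PP, but it cannot give the randomized comparison that SAP 8.1 states as its aim.

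**Precision**

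The plan gives no QoL power figure to reproduce. The inputs are 161 per arm and a 50% cross-over rate (Protocol 13.4, SAP 6); 10% and 20% are assumed for range. I assume equal SDs, complete data and no other PP exclusions. With k Controls kept:

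SE ratio (SAP 12.1 against ITT) = sqrt[(1/161 + 1/k) / (2/161)] = sqrt[(1 + 161/k) / 2]

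| Cross-over | Controls dropped | k | SE ratio |
|---|---|---|---|
| 10% | 161 × 0.10 ≈ 16 | 145 | sqrt[(1 + 1.110)/2] = 1.03 |
| 20% | 161 × 0.20 ≈ 32 | 129 | sqrt[(1 + 1.248)/2] = 1.06 |
| 50% | 161 × 0.50 = 80.5 | 81 or 80 | 1.22 or 1.23 |

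These figures apply to the EQ-5D VAS. AFEQT is given only in validated languages, so its N is smaller, and it is not stated.

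**Bias**

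Shift in the Control mean from exclusion = cross-over share × (mean change in other Controls − mean change in cross-overs).

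Each 1-point gap between those two means moves the Control mean by 0.5 point at 50% cross-over and by 0.2 point at 20%. The documents give neither the sign nor the size of the gap. Cross-overs may have done worse on drug, they may improve after ablation, and some Controls who do poorly stay because Appendix B also lists reasons to avoid cross-over.

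**Availability of data for ITT**

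Protocol 11.2.1 keeps cross-overs on their initial visit schedule, so those who have not reached the primary endpoint still have QoL visits. Subjects who reach the endpoint need return only for the 3-year visit. At the planning rates in the sample-size formula (15% Control after allowing for cross-over, 5% Test), that is 161 × 0.15 ≈ 24 Control and 161 × 0.05 ≈ 8 Test subjects by 3 years who could miss the interim QoL visits that remain.

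**The case against.** The strongest reply is that the SAP 8.1 rule allows exceptions. SAP 12.1 states one, the shells agree with it, the SAP 7 by-visit rule agrees with it, and the protocol also used PP for QoL. On this reading the plan gives one workable instruction, and a single explanatory sentence in SAP 8.1 is out of date. It is true that SAP 12.1 and the shells are consistent with each other. But the exception would cover every QoL table, and the sentence after the rule names QoL as changed and says why. For QoL the stated change would then do nothing, and SAP 12.1 gives no reason for returning to PP.

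Several smaller points stand in part:

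- The silence of SAP 5.1 is weak evidence, because that list is incomplete. For example, it omits dropping the multiple-imputation analysis of Protocol 13.10.
- The head counts assume planned enrolment and full follow-up, whereas SAP 5.1 says that the study ended early. The SE ratios depend only on the cross-over share.
- SAP 7 does not count a Control ablated after the primary endpoint as a cross-over. About 80 dropped is therefore too high if the 50% planning rate includes such ablations; the documents do not say.
- Appendix B, item 4, argues, conditionally, that cross-over would leave a younger, healthier and more compliant Control group. That could flatter Control. It is hypothetical and does not consider improvement after ablation, so the direction stays open.
- ITT does not cure missing data. Interim visits lapse after the endpoint, and at the planning rates more often in Control.

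None of these removes the contradiction or makes the SAP 12.1 comparison a randomized one.

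**Conclusion.** The concern holds. SAP 8.1 conflicts with SAP 12.1 and the eight shells on the QoL population, and only the health economics half of the stated change was carried out. The conflict rests on the text alone and on no numerical assumption.

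The between-arm QoL tests in SAP 12.1 carry selection bias that the documents do not allow anyone to sign or size. The loss of precision is small at 10-20% cross-over and material, at 22-23%, only near the 50% planning rate. QoL is a secondary endpoint and the primary analysis is untouched, so this should be corrected before QoL results are reported but does not threaten the main conclusion.

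**What to change.** In SAP 12.1, replace the two sentences on population and cross-overs with wording such as:

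> QoL is analysed in the ITT population by randomized group, with cross-over subjects kept in Control. All available QoL data are used, and the number of subjects with data is shown by arm and visit.

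Relabel Tables 14.2.11.1 to 14.2.11.5 and 14.2.12.1 to 14.2.12.3 as ITT, and list the change of QoL population in SAP 5.1. If the PP version without cross-overs is wanted, keep it as a supportive analysis labelled as non-randomized.

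State in the report that ITT QoL data are incomplete, because AFEQT covers only a language subgroup and subjects who reach the primary endpoint need not attend interim visits. State also the missing-data assumption under which the repeated measurement model is read.

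The cost is SAP wording and eight shells. No new data collection is needed: cross-overs stay on schedule, and the QoL listings (16.2.13 and 16.2.14) already cover the ITT population.

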#### 13.14.2 Quality of Life

Quality of Life (QoL) status will be compared to baseline at 3 months, 6 months, 1 year, 2 years and 3 years. QoL will be measured by the EQ-5D and AFEQT questionnaires. Descriptive statistics for the baseline and changes-from-baseline measurements of the summary scores of these two measurement scales at follow-up visits will be summarized and listed by treatment groups. The analyses will be performed in the PP population. Paired-sample test will be used to test whether the change-from-baseline values differs from zero (e.g., paired t-test) within each treatment group. A two-sample comparison of the two groups with respect to changes-from-baseline in QoL will be performed using general linear models, including the baseline value as a covariate and assessing treatment group differences.

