According to the HRS consensus statement 2017, persistent AF is defined as continuous AF that is sustained beyond 7 days. The sponsor will provide an additional adjudication using this alternative definition of time to persistent AF. Based on this additional adjudication, a sensitivity analysis for time to persistent AF based on HRS 2017 will be performed.

AFEQT

Several summary scores will be derived from the responses to questions 1 to 20 of section 2 of the AFEQT questionnaire, for each of which responses between 1 (most desirable outcome) and 7 (least desirable outcome) can be given.

Using the following statistics, the scores are defined below:

- $S(a,b)$ is the sum of responses for the range of questions between a and b (both a and b included)
- $N(a,b)$ is the number of responses given for the range of questions between a and b (both a and b included)
- AFEQT Overall Score = $100 - (((S(1,18) - N(1,18)) * 100) / (N(1,18) * 6))$
- AFEQT Symptoms Subscale Score = $100 - (((S(1,4) - N(1,4)) * 100) / (N(1,4) * 6))$
- AFEQT Daily Activities Subscale Score =
= $100 - (((S(5,12) - N(5,12)) * 100) / (N(5,12) * 6))$
- AFEQT Treatment Concern Subscale Score =
= $100 - (((S(13,18) - N(13,18)) * 100) / (N(13,18) * 6))$
- AFEQT Treatment Satisfaction Subscale Score =
= $100 - (((S(19,20) - N(19,20)) * 100) / (N(19,20) * 6))$

EQ-5D

The EQ-5D questionnaire collects the EQ-5D visual analogue scale (VAS) score on a scale between 0 and 100 and five single items (mobility, self-care, activity, pain, and anxiety) with three response levels each (no problems, some problems, extreme problems). A summary score (EQ-5D health index) based on these five items will not be calculated, as this would require rather complex modelling using country-specific weights.

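### The Wilcoxon tests on change in the EQ-5D items do not condition on the baseline level, which gives up power in a secondary quality-of-life comparison

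*SAP*

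**What the plan says.** SAP 8.3 describes five EQ-5D items with three ordered levels each and states that no EQ-5D health index will be calculated. Baseline levels are available: the protocol's assessment schedule collects the questionnaire at baseline, and SAP 12.1 says "EQ-5D single items will be summarized descriptively in a frequency table by treatment group for baseline and follow-up visits".

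For the group comparison of the items, SAP 12.1 says: "It will then be tested if there is a difference between test and control group using Wilcoxon-Mann-Whitney test separately for each follow up visit". That sentence follows the one on changes from baseline, and the planned title of Table 14.2.11.5 confirms that the test applies to the changes: "Frequency table for changes from baseline in EQ-5D single items and results of Wilcoxon-Mann-Whitney test". No covariate or stratum is named.

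The scores are handled differently. SAP 12.1 compares them "using a repeated measurement model, including the baseline value as a covariate and assessing treatment group differences". For EQ-5D, Table 14.2.11.3 limits that model to the VAS: "Results of repeated measurement model for changes from baseline in VAS". Protocol 13.14.2 plans general linear models for the quality-of-life scores, "including the baseline value as a covariate and assessing treatment group differences".

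On the population, SAP 12.1 says: "The analyses will be performed in the PP population. Cross-over subjects will be completely excluded for all QoL summaries". The table list also shows PP. SAP 8.1 says that the health-economic and quality-of-life tables were moved from PP to ITT, unless otherwise specified, so that the randomized groups are compared.

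**The concern.** On a three-level item, the change from baseline depends strongly on where the subject started. A subject with no problems at baseline cannot improve, and one with extreme problems cannot worsen. The planned test gives their zero change the same rank as the zero change of a subject who could have moved either way. The change score also carries all the noise of the baseline measurement.

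Conditioning on the baseline level removes both problems and needs no new data. Without it, a real effect on mobility, self-care, activity, pain or anxiety is more likely to be missed. Because no index is calculated, these items and the VAS are the only EQ-5D comparisons, and only the items lack baseline adjustment.

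**Working it through.** **1. Plan's own figure.** There is none to reproduce. The documents give no sample size, power, alpha or effect for the EQ-5D items. A two-sided 5% level is assumed below.

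**2. Group sizes.** SAP 6 gives 161 per arm, 10% drop-out and 50% cross-over from Control.
- Test: 161 × 0.90 = 144.9, about 145.
- Control without cross-overs: 144.9 × 0.50 = 72.45, about 72.

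**3. Expected direction.** For a continuous score with equal variance σ² at both times and correlation ρ, the change has variance 2σ²(1 − ρ). The baseline-adjusted residual has variance σ²(1 − ρ²). The ratio is 2/(1 + ρ): 1.54 at ρ = 0.3, 1.33 at 0.5 and 1.18 at 0.7. The change score is always the less efficient of the two.

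**4. Simulation for a three-level item.** Latent baseline b is standard normal. Latent follow-up is f = ρb + √(1 − ρ²)·e − δ·(Test). Both are cut at the same two thresholds to give levels B and F. The tests compared are:
- Planned: Wilcoxon-Mann-Whitney on F − B.
- Alternative: van Elteren on F within baseline level k, Z = Σ[W_k/(n_k + 1)] / √Σ[V_k/(n_k + 1)²], where W_k is the centred rank sum, V_k its variance and n_k the stratum size.

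The level shares, ρ and δ are assumptions; the documents give none of them.

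Power at 145 v 72 with δ = 0.40 SD (3,000 trials per setting):

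| Shares none/some/extreme (%) | ρ | Change test | Stratified test | Loss (points) |
|---|---|---|---|---|
| 80/18/2 | 0.3 | 26.6% | 47.2% | 20.6 |
| 80/18/2 | 0.5 | 30.2% | 48.8% | 18.6 |
| 80/18/2 | 0.7 | 38.7% | 58.0% | 19.3 |
| 60/35/5 | 0.3 | 37.4% | 60.5% | 23.1 |
| 60/35/5 | 0.5 | 45.4% | 65.2% | 19.8 |
| 60/35/5 | 0.7 | 59.0% | 74.6% | 15.6 |
| 40/50/10 | 0.3 | 45.7% | 67.8% | 22.1 |
| 40/50/10 | 0.5 | 54.7% | 73.4% | 18.7 |
| 40/50/10 | 0.7 | 68.2% | 80.3% | 12.1 |

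At δ = 0.45 SD the loss over the same correlations and mixes is about 12 to 26 points; repeat runs move the ends by about a point. For example, at ρ = 0.5 and 60/35/5%, power is about 53% v 75%.

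With 145 v 145, as if Control kept its cross-over subjects, and δ = 0.40 SD, the loss is 9 to 27 points. The direction was the same in all 18 settings (two group sizes, three mixes, three correlations).

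**5. Type I error, balanced groups.** At 145 v 72 both tests reject in about 4 to 6% of trials.

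**6. Groups that differ by 0.3 SD at baseline, no treatment effect, 145 v 72.** The result depends on how the difference behaves.

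| Behaviour of the difference | Change test | Stratified test |
|---|---|---|
| Regresses toward the mean | 8–17% | 5–7% |
| Same at follow-up as at baseline | 4–5% | 13–29% |

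**The case against.** **Materiality.** Five items at five visits give 25 tests with no stated alpha, power target or effect. Protocol 13.16 lists the quality-of-life method as descriptive statistics. SAP 2.2.3 names scores, not items, as the endpoint, and the VAS and every AFEQT score already have a baseline-adjusted model. The size of the loss rests on assumed correlations, mixes and shifts. The group sizes are planning figures, while SAP 5.1 says that the study was terminated early. All of this stands and limits the weight of the point. None of it is a reason to prefer the less efficient test.

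**Bias.** A reader might infer that stratifying by baseline level would also correct the per-protocol groups, which are no longer randomized once cross-over subjects are removed. The documents do not support that. Step 6 shows that stratification helps if a baseline difference regresses and hurts if it is stable. A stable difference is plausible: protocol Appendix B argues that those who cross over may be older and have higher HATCH scores, which would leave a younger and healthier drug group. Neither test removes selection from excluding cross-over subjects.

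**Departure from the protocol.** A reader might also infer that the item test breaks protocol 13.14.2. That section concerns the summary scores of the two questionnaires and does not mention single items, so a different method for three-level items does not contradict it. Nor does the planned test ignore baseline, since baseline is subtracted.

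**Conclusion.** The point holds as an efficiency point. The planned item tests leave out conditioning on a baseline level that is already in hand. At 145 v 72, under assumed correlations of 0.3 to 0.7, three assumed level mixes and an assumed latent shift of 0.45 SD, this costs about 12 to 26 points of power, with type I error near 5% for both tests in balanced groups. The direction is stable across the settings tried, but the size depends on the assumptions.

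No claim about bias in the per-protocol groups follows. The adjusted test is best justified in the randomized groups, so the conflict between SAP 8.1 and SAP 12.1 with its tables has to be settled alongside it. With ITT, the power argument stands and baseline imbalance is a matter of chance. The primary conclusion of the trial is unaffected.

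**What to change.** 1. In SAP 12.1 and Table 14.2.11.5, replace the Wilcoxon-Mann-Whitney test on change with a test of the follow-up item level that conditions on the baseline level. Use either a van Elteren test stratified by baseline level or a proportional-odds model with baseline level as covariate. The van Elteren test is the simpler choice if few subjects report extreme problems.
2. Keep the frequency table of changes as description.
3. State one population for quality of life and align SAP 8.1, SAP 12.1 and the table list. ITT matches the reason given in SAP 8.1 and is where the adjusted test is best justified. If PP without cross-over subjects is kept, say that baseline stratification does not make those groups comparable.

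The test change costs a few lines of SAP text and one changed SAS procedure call, with no new data. Moving the tables to ITT would mean rerunning existing programs on another population. Both should be settled before database lock.
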